2.4 Treatments (study treatment, rescue medication, concomitant therapies, compliance)

The SS will be used for all analyses associated with study treatment and medications, unless otherwise specified.

2.4.1 Study treatment / compliance

The duration of treatment for the randomized treatment phase is defined as:

Duration (days) = (date of last study treatment in randomized treatment phase – date of first study treatment) +1

The first date of study treatment is recorded on the Dosage Administration Record - At Visit (Visit 3) eCRF.

The duration of treatment for the open-label extension phase is defined as:

Duration (days) = (date of last study treatment in open-label extension phase – date of first study treatment in open-label extension phase) +1

Summary statistics will be displayed for the durations of treatment during the randomized treatment and open-label extension phases.

The durations will also be categorized into weekly time intervals (<7 days, 7 - <14 days, 14 - <21 days, ..., etc.). The number and percentage of patients in each category will be presented by treatment phase.

Total patient-days of exposure will also be summarized by treatment phase.

In addition, the number and percentage of patients at each dose level dispensed by visit will be summarized by treatment group for both the randomized treatment and open-label extension phases. The number and percentage of the maximum dose levels dispensed will also be presented by treatment group for both the randomized treatment and open-label extension phases. Similarly, the up-titrated doses, down-titrated doses and unchanged doses will be summarized by visit and treatment group for both the randomized treatment and open-label extension phases.

All information on dose administration will be listed.

2.4.2 Prior, concomitant and post therapies

Prior and concomitant medications will be coded according to the World Health Organization (WHO) Drug Reference List (v15.3 or later). The WHO Drug version will be denoted in the corresponding tables and listings. Prior and concomitant medications are mutually exclusive, as defined below:

- A prior medication is defined as any medication with an end date prior to the first dose of study treatment.
- A concomitant medication is defined as any medication taken on or after the start of study treatment. A prior medication that is 'ongoing' at the time of the first study treatment or whose end date is after first study treatment will be considered a concomitant medication.

The number and percentage of patients with prior medications will be summarized by Anatomical Therapeutic Chemical (ATC) class, preferred term and treatment group for both the randomized treatment and open-label extension phases. Concomitant medications will be summarized in a similar fashion. Separate summaries of prior ACEi and angiotensin receptor blocker (ARB) will also be produced. All medications will be listed.

The number and percentage of patients in the following prior ACEi/ARB exposure categories (assessed at screening) will be summarized:

- ACEi/ARB naïve (never exposed)
- Previously on ACEi/ARB but not currently taking (previously exposed)
- Currently taking

2.5 Analysis of the primary objective

2.5.1 Primary endpoint

The primary endpoint is the change in mean activity counts collected during the most active 30 minutes of the patient's day between baseline phase (mean of data collected each day during

Week -1) and the final randomized treatment phase measurement (mean of data collected each day during Week 8), as measured by wrist-worn accelerometer collected actigraphy (total counts per 30 minute period collected during the most active 30 minutes of each day). The analysis of the primary endpoint will be based on the FAS.

The following algorithm will be used to exclude “invalid” actigraphy data from analysis of the primary endpoint. Note that AC = activity count.

1. Isolate ‘ACTIVE’ intervals.
2. For each ‘ACTIVE’ interval, use variables [duration] and [%Invalid AC] to create a new variable [duration valid AC]. This new variable reflects the duration of valid activity data within each active period.
3. Find any [duration valid AC] that is <0.5 hours and remove it from the analysis. If an active period contains <30 minutes of valid data, then determining the most active 30 minutes within the period is not possible.
4. For each patient, sum the [duration valid AC] for each unique [Start Date] to create a new variable [all day duration valid AC]. This new variable reflects the total duration of valid activity data for each date. In most cases, each patient will have only one active period per date, but there are cases with two active periods within a single day (e.g., if patient had a nap in the middle of the day).
5. Find any [all day duration valid AC] that is <8 hours and remove all data associated with that [Start Date] from the analysis.
6. In the remaining data for analysis, each patient will have >=8 hours of valid activity data for each date. It might be one long active period, or it might comprise two shorter active periods that add up to >=8 hours.
7. For each patient, find the highest [mostActive30] for each date and use this in the analysis. In most cases, each date will have only one active period and therefore only one [mostActive30] datapoint. On dates that contain more than one active period, select the highest [mostActive30] regardless of the duration of the active period.

As long as for a single date a patient has >=8 hours of valid activity data in total, the 30 minutes with the most activity will be used in the analysis. The 8-hour threshold was selected as this requires each patient to have at least 50% of valid activity data each day, assuming 8 hours of sleep per night.

In order to calculate the mean [mostActive30] across 7 days of data during the given week, the patient must have at least 5 days of data.

2.5.2 Statistical hypothesis, model, and method of analysis

Let μ_j denote the population mean of change in mean activity count from baseline phase to Week 8 for treatment group j , $j = 0, 1$, where 0 corresponds to enalapril and 1 corresponds to sacubitril/valsartan.

The following null hypothesis (H_0) will be tested against the alternative hypothesis (H_A):

$$H_0: \mu_1 - \mu_0 = 0$$

$$H_A: \mu_1 - \mu_0 \neq 0$$

The primary endpoint will be analyzed by an analysis of covariance (ANCOVA) model with treatment and baseline activity as explanatory variables. The least squares means of the two treatment groups, least squares mean difference of the treatment groups, 95% confidence interval for the difference in the two treatment groups, and p-value based on the fitted linear model will be reported. If the p-value is <0.05 and the least squares mean difference of the treatment groups favors sacubitril/valsartan, statistical significance in favor of sacubitril/valsartan will be declared.

Before performing the above analysis, tests of normality of the variable, change in mean activity counts collected during the most active 30 minutes of the patient's day between baseline and Week 8, and the log of the variable ($\log(\text{Week 8 value}) - \log(\text{baseline value})$) will be performed. In the event the variable is not normally distributed (based on Shapiro-Wilk test p-value <0.05) but the lognormal distribution fits better, the above analysis will be performed using the log transformed data. Anti-log of the least squares mean difference of the treatment groups will be used to report the ratio of the treatment difference in the original scale.

2.5.3 Handling of missing values/censoring/discontinuations

Missing data will be imputed using the last-observation-carried-forward (LOCF) method. If a patient has no post-baseline value, the missing value will not be imputed and the patient will be removed from the analysis. If a patient's data is missing or unevaluable for the week preceding randomization, the data from the previous week will be used as the baseline measurement. If a patient's data is missing or unevaluable for each of these weeks, the patient will be excluded from the analysis.

2.5.4 Supportive analyses

A supportive nonparametric analysis will be performed to examine the consistency of results. For this supportive analysis, the primary endpoint will be analyzed using the Wilcoxon rank-sum test. The probability of one treatment being better than the other treatment will be estimated (based on the Wilcoxon rank-sum test) and the associated 95% confidence interval will be reported (Chen and Kianifard 2000).

In addition, subgroup analyses based on the FAS as described in Section 2.2.1 will be performed.

2.6 Analysis of the key secondary objective

There is no key secondary objective.

2.7 Analysis of secondary objectives

All analyses will be based on the FAS unless otherwise specified.

2.7.1 Secondary endpoints

The secondary endpoints include the following:

- Change in mean activity during sleep between baseline phase (mean of data collected during Week -1) and the final randomized treatment phase measurement (mean of data

collected during Week 8), as measured by actigraphy (activity counts per minute during daily sleep period, wrist-worn accelerometer).

- Change in mean activity during sleep between baseline phase (mean of data collected during Week -1) and each randomized treatment and open-label extension phase measurement, as measured by actigraphy (Weeks 1, 9, and 16) (activity counts per minute during daily sleep period, wrist-worn accelerometer).
- Change in mean activity counts during the most active 30 minutes of the patient's day between baseline phase (mean of data collected each day during Week -1) and each randomized treatment and open-label extension phase measurement (Weeks 1, 9, and 16), as measured by wrist worn accelerometer collected actigraphy.

Endpoints will be based on the mean of data collected for at least 5 out of the 7 days during the given week.

2.7.2 Statistical hypothesis, model, and method of analysis

During the randomized treatment phase, change from baseline for each secondary endpoint will be analyzed at each time point using the same ANCOVA model as for the primary endpoint.

During the open-label extension phase, change from baseline (mean of Week -1) for each secondary endpoint will be analyzed at each time point using paired t-tests for the group randomized to sacubitril/valsartan. The analyses will be repeated using the Week 8 measurement as baseline for the group randomized to enalapril.

2.7.3 Handling of missing values/censoring/discontinuations

For the analysis of secondary endpoints during the randomized treatment phase, the same approach for the handling of missing data as for the primary endpoint will be used (see Section 2.5.3).

2.8 Safety analyses

All safety analyses will be based on the SS unless otherwise specified. There will be no inferential analyses of the safety data.

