- All subjects that complete the 8 week double-blind treatment epoch will proceed into the 8-week open-label epoch on sacubitriI/valsartan.
- At Week 8 (Visit 8), Drug accountability will be performed and all double-blind treatment medication will be returned to the site.

- Open-label sacubitril/valsartan will be dispensed at Week 8 (Visit 8) with subject's instructions **NOT** to start their open label-treatment until after completing a 36-hour wash out. All patients will have the wash out in order to maintain the blinding of the core study.

All dose levels will be available throughout the study. Dose adjustments to lower dose levels may be made at any time at both scheduled and unscheduled visits only if indicated for blood pressure control/tolerability reasons.

All study treatment assigned by the IRT will be recorded/databased in the IRT.

All dosages prescribed and dispensed to the subject and all dose changes during the study must be recorded in the IRT and on the Dosage Administration Record eCRF.

Study medication should be taken twice daily with a glass of water with or without food.

If the subject misses taking any study drug dose, he/she should take it as soon as possible and within 4 hours of the scheduled dose time. If the patient is unable to take the missed dose within 4 hours of the scheduled dose time, he/she should skip the missed dose and return back to his/her regular study drug administration schedule.

The investigator must promote compliance by instructing the subject to take the study treatment exactly as prescribed and by stating that compliance is necessary for the subject's safety and the validity of the study. The subject must also be instructed to contact the investigator if he/she is unable for any reason to take the study treatment as prescribed.

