2.1.1 General definitions

Study treatment

Patients will receive either sacubitril/valsartan or enalapril during the first 8 weeks of the study. Study treatment will refer to either of these two drugs.

Baseline

The last non-missing assessment prior to or on the start date of study treatment (randomization date for patients not treated) will be used as baseline, unless otherwise specified.

Date of first administration of study treatment

Randomized treatment phase: The date of first administration of study treatment in the randomized treatment phase is defined as the first date a dose of study treatment is administered and recorded on the Dosage Administration Record - At Visit (Visit 3) electronic case report form (eCRF).

Open-label extension phase: The date of first administration of study treatment in the open-label extension phase is defined as the first date a dose of sacubitril/valsartan is administered in the open-label extension phase and recorded on the Dosage Administration Record - Summary eCRF.

Date of last administration of study treatment

Randomized treatment phase: The date of last administration of study treatment in the randomized treatment phase is defined as the last date a dose of study treatment is administered in the randomized treatment phase and recorded on the Double-Blind Phase Disposition eCRF (for patients continuing into the open-label extension phase) or the Study Completion/Discontinuation eCRF (for patients not continuing into the open-label extension phase).

Open-label extension phase: The date of last administration of study treatment in the open-label extension phase is defined as the last date a dose of sacubitril/valsartan is administered in the open-label extension phase and recorded on the Dosage Administration Record - Summary eCRF.

Study day

The study day describes the day of the assessment relative to the date of randomization.

The study day will be calculated as the difference between the date of assessment and the date of randomization plus 1. If the date of assessment is prior to the date of randomization, the study day will be negative and will be calculated as the difference between the date of the assessment and the date of randomization.

Randomized treatment phase

Assessments performed at Weeks 2, 4, or 8 (e.g., vital signs) are assigned to the randomized treatment phase for summarization purposes. Unscheduled assessments are not assigned to a phase.

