For summarization of adverse events [AEs], medications, protocol deviations, and notable vital signs and laboratory abnormalities by treatment phase, an assessment during the randomized treatment phase is defined as any assessment obtained in the following time interval:

Date of randomization (or date of first administration of study treatment, as appropriate) through the date of the Week 8 visit, inclusive.

Open-label extension phase

Assessments performed at Weeks 10, 12, or 16 (e.g., vital signs) are assigned to the open-label extension phase for summarization purposes. Unscheduled assessments are not assigned to a study phase.

For summarization of AEs, medications, protocol deviations, and notable vital signs and laboratory abnormalities by treatment phase, an assessment during the open-label extension phase is defined as any assessment obtained in the following time interval:

After the date of the Week 8 visit.

Last contact

The date of last contact will be the last visit date for each patient and will be derived by examining all visit data collected in the eCRFs.

Year, month and week

For reporting purposes, the rules below will be followed to convert a year, month and week to days.

1 year = 365.25 days

1 month = 30.3475 days

1 week = 7 days

1 day = 24 hours

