2.2 Analysis sets

The following analysis data sets will be used in the analyses:

Randomized Set (RS): The RS will consist of all randomized patients.

Full Analysis Set (FAS): The FAS will consist of all randomized patients with the exception for those patients who have not been qualified for randomization and have not received study treatment, but have been inadvertently randomized into the study. Following the intent-to-treat principle, patients will be analyzed according to the treatment to which they were assigned at randomization. Efficacy variables will be analyzed based on the FAS as the primary set.

Safety Set (SS): The SS will consist of all randomized patients who have received at least one dose of study treatment. Patients will be included in the analysis according to the treatment actually received. The SS will be used for the analyses of safety variables.

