2.8.1.2 General rules for AE reporting

AE summaries will include all treatment-emergent AEs (TEAEs). TEAEs are defined as AEs starting on or after the first day of study treatment. All AEs will be listed. AEs starting prior to the first day of study treatment (non-TEAEs) will be flagged in the listings.

All TEAEs will be summarized by treatment phase as defined in Section 2.1.1.

TEAEs will be summarized by presenting the number and percentage of patients having at least one TEAE, having at least one TEAE in each primary SOC, and for each PT using MedDRA terminology. A patient with multiple occurrences of a TEAE will be counted only once in the AE category.

Separate summaries will be presented by SOC, PT and severity. A patient with multiple severities for an AE will be summarized under the worst severity recorded for the event.

Any information collected will be listed as appropriate.

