5.6 Rule of exclusion criteria of analysis sets

Table 1 Protocol deviations that cause patients to be excluded

Deviation ID	Description of Deviation	Exclusion in Analyses
NA	NA	NA

Table 2 Patient Classification

Analysis Set	Protocol deviation ID that cause patients to be excluded	Non-protocol deviation criteria that cause patients to be excluded
RS	NA	Not randomized
FAS	NA	Not in RS; Have not received study treatment but inadvertently randomized
SS	NA	No double-blind study treatment received

6 Reference

Chen M, Kianifard F (2000) A nonparametric procedure associated with a clinically meaningful efficacy measure. *Biostatistics*; 1(3):293-298.

[REDACTED]

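### The SAP defines no open-label safety set, so phase-level open-label percentages would be divided by patients who never took open-label drug

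*SAP*

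**What the plan says.** SAP 2.8 sets the default population: "All safety analyses will be based on the SS unless otherwise specified". SAP 2.2 defines it: "The SS will consist of all randomized patients who have received at least one dose of study treatment". SAP 2.1.1 ties study treatment to the randomized drugs: "Patients will receive either sacubitril/valsartan or enalapril during the first 8 weeks of the study". Table 2 in SAP 5.6 gives a single reason for exclusion from the Safety Set (SS): "No double-blind study treatment received". Neither SAP 2.2 nor protocol 9.1 defines a set based on open-label dosing.

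SAP 2.8.1.2 then requires that "All TEAEs will be summarized by treatment phase as defined in Section 2.1.1", by "presenting the number and percentage of patients having at least one TEAE". Notable laboratory values (SAP 2.8.3), notable vital signs (SAP 2.8.4.1) and angioedema data (SAP 2.8.4.3) are also reported as numbers and percentages by phase. SAP 2.4 applies the SS to exposure, where duration categories are percentages by phase (SAP 2.4.1).

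For adverse events and notable values, SAP 2.1.1 defines the open-label phase by date alone: "After the date of the Week 8 visit". On entry to that phase, protocol 5.5.4 says: "All subjects that complete the 8 week double-blind treatment epoch will proceed into the 8-week open-label epoch on" sacubitril/valsartan. Under protocol 5.6.2, a patient who stops study drug early returns for an end-of-study visit.

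**The concern.** A percentage for the open-label phase should describe patients who were exposed in it. The stated rule divides instead by everyone dosed in the double-blind phase. A patient who left before Week 8 has no Week 8 visit date, hence no open-label window and no possibility of a counted event, yet remains in the denominator. The percentage is pulled down, and by more in an arm with more early stopping.

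The quantity matters in this design. Patients randomized to enalapril first receive sacubitril/valsartan in open label, and protocol 3.6 gives angioedema risk as the reason for the washout before that phase. Incidence among patients actually exposed is what a safety reader would look for.

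**Working it through.** **Inputs**
- 136 randomized, 1:1, so 68 per arm (protocol 9.8, 5.2 and Table 5-1).
- 20% drop-out and 10% non-evaluable, difference 5000, SD 7400, two-sided 0.05 (protocol 9.8 and 9; SAP 3 and 2.1).
- Assumption: all 136 take a double-blind dose, so N(SS) = 136.
- Not in the documents: the number who take open-label drug, N(OL). Protocol Table 5-3 lists 136 and makes no allowance for drop-out.

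**The plan's own figure.** The 20% appears only in the power statements. With n per arm = 136 × (1 − 0.20 − 0.10) / 2 = 47.6, power = Φ(5000 / (7400 × √(2/47.6)) − 1.96) = Φ(3.30 − 1.96) = 90.9% (90.4% with the t distribution). Applying the two losses in turn, n = 136 × 0.8 × 0.9 / 2 = 48.96, which gives 91.7% (t: 91.1%). The stated 90% is reproduced. The 20% is therefore a planning rate for the Week 8 comparison, not a stated rate of open-label non-entry.

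**Dilution.** If x open-label-treated patients have an event,

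x / N(SS) = [x / N(OL)] × [N(OL) / N(SS)],

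so the dilution factor is N(OL) / N(SS).

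- All enter: 136/136 = 1, no dilution.
- Assumed 5% non-entry: 129/136 = 0.95.
- All of the 20% drop-out before open label: 136 × 0.80 = 108.8, about 109; 109/136 = 0.80.
- Assumed 30% non-entry: 95/136 = 0.70.

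At 109 entrants, 11 patients with an event are 11/109 = 10.1% of those exposed but 11/136 = 8.1% of the SS; 22 patients are 20.2% and 16.2%.

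**Unequal stopping (assumed).** With 10% non-entry in one arm and 30% in the other, and a true open-label rate of 10% in both, the tables would show 0.10 × 0.90 = 9.0% and 0.10 × 0.70 = 7.0%. The denominator alone creates that difference.

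**Which outputs are affected**
- Affected: phase-level percentages for TEAEs, SAEs, notable laboratory and vital-sign abnormalities, angioedema and exposure-duration categories.
- Not affected: by-visit means and changes, which rest on patients with data, and total patient-days, to which non-entrants contribute nothing.
- Outside the SS rule: deaths, which SAP 2.8.2 places on the FAS.

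**Numerator.** Because the window is a date rule, an event in the 36-hour washout counts as open-label even if the patient never starts open-label drug. This can offset the dilution slightly, but it means that numerator and denominator describe different patients. Changing the denominator alone would leave such an event in the open-label phase for a patient outside the new set.

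**The case against.** The strongest reply is that SAP 2.8.1.2 asks for a percentage without naming its divisor, so the denominator is unstated rather than wrong, and the table shells, which are not among the documents, may use the number who entered. It is true that the shells could do so. But SAP 2.8 is a default that holds unless something else is specified, and nothing else is specified for these tables. The SAP mentions the shells only for details of the primary model. Counting patients who continue into open label in the disposition table (SAP 2.3.1) does not make them an analysis set.

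Second, the consequences are limited, and this stands. Safety is descriptive, all open-label patients receive the same drug, and a reader could rescale using the disposition count.

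Three stronger readings are tempting, and the documents do not support them.
- A reader might infer that every open-label percentage is 20% too low. The 20% is borrowed from the Week 8 power calculation, and by-visit summaries and patient-days are not diluted. The laboratory shift tables in SAP 2.8.3 are described in terms of patients with laboratory values, so they are not counted here either.
- A reader might infer that events would drop out of the table of most frequent AEs (5% or more). With denominators of 136 and 109 the cut-off needs 7 and 6 patients (0.05 × 136 = 6.8; 0.05 × 109 = 5.45), so only a count of exactly 6 changes status. SAP 2.8.1.3 does not say whether the cut-off applies by phase, by arm or overall, and the event would still appear in the full SOC/PT table.
- A reader might infer that the right denominator would make open-label and double-blind percentages comparable. It would not, because open-label entrants are a selected group of double-blind completers.

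**Conclusion.** The point holds for phase-level open-label incidence and exposure percentages. As written, the SAP divides them by a set defined by double-blind dosing, and they would be understated by the share of that set that never takes open-label drug. The relative understatement is about one fifth if the planned 20% drop-out all falls before open label, 5% to 30% over the assumed range of non-entry, and nil if all enter. These figures assume that all 136 patients are dosed in the double-blind phase and that the tables follow the SAP text. A difference between arms would need unequal early stopping, which is hypothetical. No hypothesis test, error rate or efficacy result is affected. The correction is still worth making: the descriptive percentages are the whole of the planned safety result, and the remedy is simple.

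**What to change.** 1. In SAP 2.2 and Table 2, add an Open-Label Safety Set: all randomized patients with at least one dose of open-label sacubitril/valsartan.
2. In SAP 2.4 and 2.8, name it as the denominator for phase-level open-label incidence and exposure tables, by randomized group where the table is split that way. Keep the SS for the double-blind phase.
3. In SAP 2.1.1, start the open-label summary window at the first open-label dose and assign events between the Week 8 visit and that dose to the randomized phase. For a patient with no open-label dose, treatment-emergent events then stay in the randomized phase. The same window serves medications and protocol deviations, so state whether the change applies to them too.

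The cost is SAP wording, one population flag, and reprogramming of the window and the column totals in the tables concerned. No new data are needed, because SAP 2.1.1 already defines the first open-label dose date from the dosage record.
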